### e) Study Endpoints

The primary endpoint is return to baseline cognitive function.

### f) Procedures Involved in the Human Research

Cognitive testing, administration and monitoring of anesthesia, MRI

As the participants in the study are volunteers, we will be in touch with their PMD if they have one. Upon discharge from the hospital, subjects will be provided with a card that will remind them of their next appointment as well as who to contact in case of emergency related to this study.

### g) Specimen Banking

|   |   |   |  |
|---|---|---|--|
| 
Mount
Sinai | Protocol Title:                           | Trajectory of Recovery in the Elderly                                   |  |
|   | Principal Investigator Name/Contact Info: | [name]
[contact]                       |  |
|   | Primary Contact Name/Contact Info         | [name] [contact]
[contact] |  |
|   | Date Revised:                             | 02/23/2018  |  |
|   | Study Number:                             | GCO 13-0359   |  |
|   |   |   |  |

Blood specimens will be drawn for biomarker analysis. The specific biomarkers will be the subject of another grant submission.

"Specimens will be stored for no more than 5 years. The specimens will only be accessed based on a specifically approved IRB protocol.

Participants will be allowed to have their specimens either de-identified or destroyed."

### **h) Data Management and Confidentiality**

Data will be maintained either on paper forms or within database secured behind the MSSM firewall

### **i) Provisions to Monitor the Data to Ensure the Safety of subjects**

Provisions to monitor the data to ensure the safety of subjects is undertaken by at least three means.

- 1) The patients will be highly selected and subsequently monitored during the procedure
- 2) We have designed a format for focused enrollment to support an early safety assessment after 10 subjects between 70-80 have completed their assessments
- 3) Although not a clinical trial, a Data and Safety Monitoring Board has been approved by the National Institute on Aging to monitor this study and will undertake their first evaluation after 10 patients have completed the protocol.

To ensure the feasibility of the study and as a further safety precaution, we will first enroll 10 persons in the 70-80 year old range and follow the study protocol. These results will be closely monitored for any adverse events. Should any participant not return to their baseline POSTOP-QRS by 30 days the DSMB will be notified. This design ensures that we will demonstrate that it is feasible to recruit in this age range and that volunteers are able to conduct all steps of the protocol safely.

Patients who are enrolled in the protocol will have an initial anatomical MRI. The clinical neuroradiologist on this study ([name]) will review this anatomical scan prior to the initiation of anesthesia. Any lesion or finding that would indicate additional risk to proceeding will cause the protocol to cease. Any incidental findings on MRI will be reported to the participant as per the standard incidental finding procedures in place for all imaging studies at Mount Sinai. Briefly, in the presence of incidental finding the preference is to present the information to the participant in collaboration with their primary care physician. In the absence of a

|   |   |   |
|---|---|---|
| 
Mount
Sinai | Protocol Title:                           | Trajectory of Recovery in the Elderly                                   |
|   | Principal Investigator Name/Contact Info: | [name]
[contact]                       |
|   | Primary Contact Name/Contact Info         | [name] [contact]
[contact] |
|   | Date Revised:                             | 02/23/2018  |
|   | Study Number:                             | GCO 13-0359   |
|   |   |   |

primary care physician, we will arrange a consultation with the neuroradiologist and provide a primary care referral.

The principle methodology to minimize the risk of drug administration will be to monitor the patient within the MRI suite by a team of at least two trained anesthesia personnel. To minimize the risks we have obtained a state-of-the-art MRI compatible anesthesia monitor which provides ECG, pulse oximetry, automated blood pressure, continuous capnography and gas concentration evaluation. As the research MRI suite is at some distance from the regular operating rooms, our protocol requires the presence of least two anesthesiologists at each session. Vital signs are assessed and recorded at a minimum of every 5 minutes. Research personnel familiar with all aspects of the protocol will be involved in the anesthetic and PACU care of all participants.

Dosing of all anesthetics is altered in an age appropriate manner. For propofol, the standard induction dose is 2.5 mg/kg. For elderly patients, the accepted range is 1.5-1.8 mg/kg. Furthermore, as the point of the current use of induction agent is merely to have a rapid induction for the insertion of the laryngeal airway, the dose is titrated to effect to achieve the needed state with the minimum amount of medication.

For sevoflurane, the age adjusted minimal alveolar concentration of MAC (volatile equivalent of an ED50) decreased with age. For the current study, the participants are all administered sevoflurane to a processed EEG level of 40-60. This ensures a similar level of anesthetic depth in all participants and, based on extensive experience, the amount of anesthetic needed to achieve these levels will be similar to the age adjusted MAC." During the resting state scan the anesthesiologist will manage the sevoflurane as follows: 15 min 1MAC (baseline), 15 min 1.5 MAC (increased), 1 MAC (return to baseline), deviation from this protocol for the safety of the individual will be determined by the anesthesiologist during the procedure.

Volunteers who undergo the complete protocol, including the anesthesia, will be brought to a (PACU) where their recovery will be supervised by regular PACU nursing staff. PACU nurses will be in-serviced to assure familiarity with the protocol. Discharge from the PACU is determined by an algorithm that was modified from the Aldrete criteria. In addition, volunteers are required by hospital policy to have a competent adult to accompany them from the hospital back to their home.

|   |   |   |
|---|---|---|
| 
Mount
Sinai | Protocol Title:                           | Trajectory of Recovery in the Elderly                                   |
|   | Principal Investigator Name/Contact Info: | [name]
[contact]                       |
|   | Primary Contact Name/Contact Info         | [name] [contact]
[contact] |
|   | Date Revised:                             | 02/23/2018  |
|   | Study Number:                             | GCO 13-0359   |
|   |   |   |

The PACU discharge criteria in use for this study are the same criteria used for discharging all standard surgical patients. In essence, these are a modification of the Aldrete criteria (see below). This system is employed by the PACU nurses, who make the determination of when patients are ready to proceed to either second stage recovery or home.

#### Respiration

2= Able to take deep breath and cough

1= Dyspnea/shallow breathing

0= Apnea

#### O2 Saturation

2= Maintains >92% on room air

1= Needs O2 inhalation to maintain O2 saturation >90%

0= Saturation < 90% even with supplemental oxygen

#### Consciousness

2= Fully awake

1= Arousalable on calling

0= Not responding

#### Circulation

2= BP+ 20mm HG pre op

1= BP+ 20- 50 mm HG pre op

0= BP+ 50mm HG pre op

#### Activity

2= Able to move 4 extremities

1= Able to move 2 extremities

0= Able to move 0 extremities

The total score is 10. Patients scoring > 8 (and/or are returned to similar pre op status) are considered fit for transition to Phase II recovery"

If a patient has persistent issues, we will continue to follow the patient. If there is any concern regarding change in cognitive function, we have the ability to refer the patient into formal assessment by the ADRC."

|   |   |   |
|---|---|---|
| 
Mount
Sinai | Protocol Title:                           | Trajectory of Recovery in the Elderly                                   |
|   | Principal Investigator Name/Contact Info: | [name]
[contact]                       |
|   | Primary Contact Name/Contact Info         | [name] [contact]
[contact] |
|   | Date Revised:                             | 02/23/2018  |
|   | Study Number:                             | GCO 13-0359   |
|   |   |   |

Risks associated with the neuropsychological testing will be minimized by extensive training of the research assistants, with particular focus on sensitivity to the patient's condition. Confidentiality and privacy will be maintained by initial and continuing education of the research staff, as well as proper design of all procedures.

Although this is not a clinical trial, we will have a Data and Safety Monitoring Board that will meet via teleconference after the first 10 volunteers aged 70 to 80 years old and at a minimum of twice per year. The DSMB will evaluate all unanticipated events and safety if volunteers are not found to return to baseline POSTOP-QRS function by 30 days.. All adverse and unanticipated events will be reported to the IRB as well as to the DSMB.

All of our databases are kept on the research drive which is maintained by IT and is behind Sinai's firewall. The coordinators and the anesthesia investigators will have access to the full information. As the data are behind the fire wall, they will contain identifying information. That is necessary because we have to find the participant at intervals to follow up on the testing scheme. The data will be stored for 6 years after the study is complete.

Drs. [name] and [name] will be the Mount Sinai Principal monitors.

#### **j) Withdrawal of Subjects**

Participants may withdraw at any time. Standard procedure for all anesthetics is to perform a postoperative evaluation, usually by phone, within 48 hours. If a participant decides to drop out, we will inquire as to whether we can maintain their information that we have to date. If they say no, we will destroy their information.

#### **6) Risks to Subjects**

The risks directly attributed to the administration of general anesthesia have decreased markedly with provision of intensive continuous monitoring. Direct anesthetic morbidity and mortality is estimated at less than 1 in 450,000 cases. We believe that, in the absence of surgical stress that there is an extremely low risk of cognitive dysfunction. Both our experience in which cognitive dysfunction is transient and recent animal data suggest that there is more than adequate clinical equipoise to justify the proposed study.

There are minor risks associated with the placement of the intravenous catheter, placement of the airway device and conduct of the cognitive

|   |   |   |  |
|---|---|---|--|
| 
Mount
Sinai | Protocol Title:                           | Trajectory of Recovery in the Elderly                                   |  |
|   | Principal Investigator Name/Contact Info: | [name]
[contact]                       |  |
|   | Primary Contact Name/Contact Info         | [name] [contact]
[contact] |  |
|   | Date Revised:                             | 02/23/2018  |  |
|   | Study Number:                             | GCO 13-0359   |  |
|   |   |   |  |

tests. There is a risk of reaction to the enclosed space of the MRI machine.

Once patients are anesthetized, a laryngeal mask airway (LMA) will be placed in the back of their mouth to allow them to breathe on their own during the two hour general anesthetic. This device will be placed by an experienced anesthesiologist. The LMA is very safe, but has risks associated with it. The estimated rate of critical incidents associated with the LMA is 15 in 10,000 anesthetics (0.15%). Risks of the LMA when used for general anesthesia include:

- Aspiration (entry into your lungs) of stomach contents
- Pressure-related injury of your mouth and throat
- Laryngospasm (temporary closure of your vocal chords)

Risks to privacy and confidentiality for this small pilot study are very low. All data will be guarded as for any study involving human subjects.

## 7) Provisions for Research Related Injury

A physician will be responsible for the patient during their anesthesia and will immediately respond to all problems. As the majority of problems related to anesthesia (e.g. allergy) occur at that time, the anesthesiologists will be the physicians to manage the issues. Should the participants develop any other injury identified during follow up, they will be referred to an appropriate physician.

Should anyone have significant delirium/cognitive impairment or other medical complications from the study, they will be admitted, and the costs of the admission will be borne by the study."

## 8) Potential Benefits to Subjects

There is no benefit to participants in the study

## 9) Provisions to Protect the Privacy Interests of Subjects

The identity of all participants will be maintained confidential. No information will be shared outside of the medical center. All information will be maintained in secure form within Mount Sinai

## 10) Economic Impact on Subjects

There should be no economic impact on subjects

## 11) Payment to Subjects

|   |   |   |
|---|---|---|
| 
Mount
Sinai | Protocol Title:                           | Trajectory of Recovery in the Elderly                                   |
|   | Principal Investigator Name/Contact Info: | [name]
[contact]                       |
|   | Primary Contact Name/Contact Info         | [name] [contact]
[contact] |
|   | Date Revised:                             | 02/23/2018  |
|   | Study Number:                             | GCO 13-0359   |
|   |   |   |

Each participant will be given up to \$600 for participating in the project. Reimbursement will be paid as follows; \$300 for the initial day of anesthesia and MRI work, \$300 after the 1 month post op assessment is completed.

Transportation to and from Mount Sinai will be provided for the participants at no cost to them for visits which require that they return to Mount Sinai.

## 12) Consent Process

Participants who contact the research group will be given an explanation of the project by one of the study investigators and provided with a copy of the consent form. If the potential participant desires, a time will be arranged for the participants to meet with the investigator and discuss the process. After all questions are answered, the participant will be asked if he or she wants to participate. If they believe that the project is right for them and that they understand the risks of the project, they will be asked to provide documentation of their consent by signing an IRB approved consent form

## 13) Process to Document Consent in Writing

We will use a standard IRB approved consent form and standard MSSM procedures for obtaining and documenting informed consent

## 14) Vulnerable Populations

Vulnerable populations will not be included in this pilot study

"It is extraordinarily important for safe conduct of this study that cognitively intact and healthy individuals are included in this protocol. To achieve these ends we:

1) Are including only volunteers. Our experience to date is that individuals who volunteer are cognitively intact although we did exclude potential participants in the pilot study for medical issues (asthma and hypertension) No surrogate consents are permitted.

2) The potential participants have to engage with our research group to go through the informed consent process. As in the pilot study, our coordinators, all of whom have extensive experience in delirium screening (under the supervision of [name], Liaison Psychiatry at Yale) and cognitive assessments (under the supervision of [name] and [name]), so they are extremely experienced with concepts of normal and abnormal. They are clearly aware of the need to have cognitively intact patients and will not pursue the consenting process for

|   |                        |  |
|---|------------------------|--|
| 
Mount
Sinai | Protocol Title:        | Trajectory of Recovery in the Elderly  |
|   | Principal Investigator | [name]  |
|   | Name/Contact Info:     | [contact]         |
|   | Primary Contact        | [name] [contact] |
|   | Name/Contact Info      | [contact]       |
|   | Date Revised:          | 02/23/2018   |
|   | Study Number:          | GCO 13-0359  |

anyone who is not 100% clear on the project. This is as opposed to previous studies in which we were specifically looking for patients who had Mild Cognitive Impairment, where the challenge was to be sure the patient understood enough to participate.

3) Once a volunteer clearly understands and agrees to participate, they undergo a series of cognitive tests (POSTOP-QRS, paper and pen cognitive test and NIH Toolbox). Inability to complete these tests or significantly impaired results on this test will be brought to the attention of the investigators who can recommend that the participant be excluded.

4) All participants will be examined by a board certified anesthesiologist who will discuss the patient's medical history, perform and examination and go over the requirements of the protocol. Any indication that the volunteer does not meet inclusion criteria will result in a determination for not proceed to imaging and anesthesia

5) Finally, if all of the above are consistent with the protocol, the participant will have their baseline MRI. The baseline MRI will be read by [name] before the protocol proceeds to the induction of anesthesia. Any signs of occult CNS disease will cause the protocol to be aborted.

**15) Multi-Site Human Research (Coordinating Center)**

N/A

**16) Community-Based Participatory Research**

N/A

**17) Sharing of Results with Subjects**

Participants will be offered the opportunity to discuss their test results if they desire. The testing battery employed is not particularly clinically relevant in the sense that it is not designed to diagnose cognitive problems, so the value is primarily for curiosity

**18) IRB Review History**

A pilot study was conducted prior to the submission of this project. This project is similar in nature.

**19) Control of Drugs, Biologics, or Devices**

*Note: The IDS has its own forms that must be completed and a review process that must be followed before the IDS representative will sign off on Appendix B for submission to the PPHS.*

|   |   |  |  |
|---|---|--|--|
| 
Mount
Sinai | Protocol Title:                           | Trajectory of Recovery in the Elderly  |  |
|   | Principal Investigator Name/Contact Info: | [name]
[contact]  |  |
|   | Primary Contact Name/Contact Info         | [name] [contact]
[contact] |  |
|   | Date Revised:                             | 02/23/2018   |  |
|   | Study Number:                             | GCO 13-0359  |  |

Sevoflurane and propofol will be obtained from the standard sources. Sevoflurane is maintained by the anesthesia department in restricted but not secure areas (anesthesia workroom). Propofol is maintained by the pharmacy and will be obtained from through the research pharmacy.

Trajectory of Recovery in the Elderly (TORIE)

PI: [name]

NCT02275026

Document Date: 10-31-2013

protocols and forms will be compiled into an operations manual that will be revised as necessary. The manual will include a question-by-question written script for interviewing purposes. Neuropsychological assessment will be conducted by specially trained personnel with experience in psychological assessment. Training will be conducted, as part of the overall investigators' training meeting, by Drs. [name]. Training seminars will be repeated every six months and as needed, to ensure standardization of procedures.

Data Reliability: Diagnostic, case ascertainment and methodologic consistency will be assured by implementing at least every six month training sessions for all the staff. An initial training meeting before study enrollment, and monthly conferences thereafter will ensure reliability and consistency in the use of diagnostic criteria and written standard operating procedures. All data will be independently audited to confirm consistency among participant records, study data sheets, and the main database. Additionally, we will use standard statistical and graphical methods to identify outlying data and confirm their validity

Data will be maintained in a custom-designed relational database (Research Electronic Data Capture REDCap). The REDCap Consortium is composed of 549 active institutional partners from CTSA, GCRC, RCMI and other institutions in 50 countries. The consortium supports a secure web application (REDCap) designed exclusively to support data capture for research studies.

Although the current proposal is not a clinical trial, we will incorporate a **Data and Safety Monitoring Plan** with a **Data and Safety Monitoring Board** (DSMB) as described in the section E.

10. Data Analysis

All analyses will use a type I error of 5% (two-sided) to test for statistical significance, and will be performed using SAS v9.3 (SAS Institute Inc., Cary, NC). The fit of all models to the data will be examined using standard approaches, such as examination of residuals and the proportional hazards assumption for Cox regression. All baseline and outcome data on participants enrolled in this study will be summarized. Categorical variables will be described in terms of counts and percentages, and quantitative variables in terms of medians and ranges or means and standard deviations, as appropriate.

10.1 Specific Aim I: *The primary goal is to test whether age is associated with the time of return to baseline cognitive function, assessed by PQRS (primary) and NIH toolbox (secondary), following general anesthesia.*

Scales of the PQRS are performed prior to anesthesia, and then following anesthesia at defined time intervals (see Section 4). We will focus on the recovery of cognitive function (the primary endpoints as described in 5.0) as related to age and controlling for other participant characteristics using Cox discrete time regression.⁷⁴ We expect that everyone will return to baseline cognitive function by 30 days, most early in the course of testing. Thus, if later time points are missing most will have been observed before loss to follow-up. For intermittent missingness before returning to baseline, we will truncate the observations at the time of missing observations. In a subsequent sensitivity analysis, we will assume that they are missing at random and use last value carried forward (worse-case scenario). We will also explore multiple imputation if >5% of the outcome data are missing prior to returning to baseline function.

For the secondary NIH Toolbox outcomes, we will calculate six primary standard Adjusted Scale Scores, as described in the Scoring Manual for Toolbox measures described in 5.1. We will again use discrete time Cox regression with covariate adjustment; however, the granularity of the timing of measurements is less than the primary outcome of PQRS. For both the primary and secondary outcomes, we will use the Hochberg test to adjust for multiple comparisons.⁷⁵

To study the time course of the PQRS and Toolbox measures, we will use generalized linear mixed models (GLMMs),⁷⁶ which account for the covariance structure of repeated observations within participant, and we will test whether a random intercepts and slopes for participants best fit the data. GLMMs are statistical models for data with correlations or non-constant variability and where the response is not necessarily normally distributed. GLMMs assume that missing data are missing at random; thus, participants with partial data contribute to the model estimation. We will fit the appropriate distribution (e.g. dichotomous, count, ordinal, normal) for each outcome using Proc GLIMMIX in SAS v9.3.

10.2 Specific Aim II: *The measures for fMRI analyses generally fall into three groups: resting, task-driven, and rCBF.*

Change scores will be calculated for each of 20-25 components (characterizing resting state and activity driven brain networks) related to fMRI imaging at each time point (Section 4). These changes (expressed in standardized units) associated with age will be analyzed using GLMMS adjusted for participant characteristics as described for Aim 1. We will use the False Discovery Rate test to adjust for multiple comparisons.⁷⁷

For the ASL analysis, an additional 5 measures for rCBF (global and right/left frontal and temporal) will be generated for each of three time points and analyzed with GLMMS corrected for multiple comparisons as described above.

fMRI components will be entered as covariates in the above-mentioned Cox discrete-time models for the primary outcomes (PQRS and NIH Toolbox scales) to assess their association with the primary outcomes and with age. Similarly, the fMRI components will be entered into the GLMMS described in 10.1 to estimate their adjusted associations. We will use the False Discovery Rate test to adjust for multiple comparisons.⁷⁷

10.3 Sample Size, Power, and Effect Size Estimation:

Sample and power for secondary outcomes were calculated with PASS12 (PASS12, Kayville, Utah, USA). **SA1:** A Cox regression⁷⁸ on the time to return to baseline cognitive performance requires 72 participants to detect a HR of 1.03 per year or age ($\beta=0.033$), assuming a standard deviation for age of 11.25 years, 80% power, a Type I error of 0.05, and adjusting for other characteristics expected to have a generalized R^2 of 0.2.⁷⁹⁸⁰

The NIH toolbox yields six primary standardized scaled scores (mean=100, SD=15). Although there will be fewer discrete time measurements for Cox regression, the effect-size calculation is similar. Assuming 72 participants with a standard deviation for age of 11.25 years, an adjusted Type 1 error rate of $0.05/6=0.0083$, and other covariates having a generalized R^2 of 0.2 with age, a HR of 1.04 ($\beta=0.041$) can be detected with 80% power.⁸⁰

SA2: A sample size of 72 maintains 80% power for 30 MRI components to detect a change of 0.04 in each component testing for variation across the age spectrum where the assumed standard deviation of age is 11.25 years, the SD of the normalized MRI component outcomes is 1.0, and the two-sided Type I error of 0.0017 to account for multiplicity of the 30 tests (Bonferroni correction). We recognize that in fMRI, multiple comparisons across massive numbers of voxels make it extremely difficult to formulate valid assumptions regarding variability. However, we are using summary measures for these components and have used a Bonferroni adjustment for power calculation.

We expect missing data to be low as the total time under observation is 30 days and all participants are expected to have returned to baseline cognitive function by 30 days. Preliminary data had 75% return to baseline at T+15 minutes and all by 7 days. Thus, outcomes are expected to be captured on the majority of subjects even if they do not attend all follow-up visits. However, to insure sufficient outcomes we will increase by 5.5% to 76 thus adding a participant to each age decade.

11. Scientific Limitations and Rationale for Design Decisions

The results will be a first step and cannot completely elucidate age-related differences in subjects and conditions associated with clinical indications for surgery. The study focuses on the main effect of anesthesia on cognitive recovery but cannot address the possibility that administration of anesthesia interacts in some way with what happens due to the surgery itself. There are multiple anesthetics in current use. This proposal includes a fairly standard combination of anesthetic agents. Additional agents cannot be accommodated in this model. Safety is a primary concern. The current design is focused on safety as opposed to results at any cost.

There are multiple alternative means of assessing the central nervous system apart from cognitive testing and MRI based imaging. The investigators considered using PET scanning for amyloid and EEG as an assessment of cerebral function. While each of these presents an advantage, neither could be accommodated in the current design. PET scanning involves further risk of radiation exposure. EEG in the context of MRI is not available in our institution at this time (we are working on it). EEG as a primary alternative is possible. The choice of MRI represents a decision by the investigators as to the most likely scientific benefit.

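### Truncating the PQRS record at a missed pre-recovery visit wastes returns seen later, and the carry-forward sensitivity analysis is mislabelled as missing at random; the loss is of efficiency and is small

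*SAP*

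**What the plan says.** The primary Aim I analysis (SAP 10.1) is a discrete-time Cox regression of time to return to baseline PQRS cognitive function on age, with covariates. For gaps before recovery the main rule is: "For intermittent missingness before returning to baseline, we will truncate the observations at the time of missing observations". The sensitivity analysis follows: "we will assume that they are missing at random and use last value carried forward (worse-case scenario". A further step is conditional: "We will also explore multiple imputation if >5% of the outcome data are missing prior to returning to baseline function".

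The SAP gives reasons for expecting little trouble. In 10.1: "Thus, if later time points are missing most will have been observed before loss to follow-up". In 10.3: "We expect missing data to be low as the total time under observation is 30 days", "Preliminary data had 75% return to baseline at T+15 minutes and all by 7 days", and "Thus, outcomes are expected to be captured on the majority of subjects even if they do not attend all follow-up visits". Section 10.3 also raises the sample from 72 to 76 to protect the number of outcomes. For the secondary time-course models, 10.1 says: "GLMMs assume that missing data are missing at random; thus, participants with partial data contribute to the model estimation".

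The schedule in Protocol 5d places the PQRS before the procedure and then at T+15, T+40, days 1, 3, 7 and 30, and 6 months. T+15 is the first assessment after anesthesia. T+15 and T+40 are both done on site.

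**The concern.** Intermittent missingness means that later visits exist. Take a participant who is not recovered at T+15, is missed at T+40 and is recovered on day 1. The return is known to lie between T+15 and day 1, yet under the rule the record stops at T+40 and the return is not used. The SAP's reassurance that outcomes are captured despite missed visits holds for visits missed after recovery. Under truncation it does not hold for a visit missed before recovery.

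The sensitivity analysis has a separate fault. Missing at random and single-value carry-forward are different assumptions, so one analysis cannot be described as both. Carrying a not-recovered status forward fits the worst-case label. At T+15, however, there is no earlier post-anesthesia value to carry.

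At stake are some power in the primary test of age, and a sensitivity analysis whose result would be hard to interpret.

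**Working it through.** **1. The SAP's own figure.** Inputs from SAP 10 and 10.3: two-sided alpha 0.05, power 80%, SD of age 11.25 years, beta 0.033 per year, R² 0.2, and every participant an event.

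N = (z₀.₉₇₅ + z₀.₈₀)² / [SD² × beta² × (1 − R²)] = 7.849 / (126.5625 × 0.001089 × 0.8) = 7.849 / 0.11026 = 71.2, rounded up to 72. This matches the SAP. The inflation is 72 × 1.055 = 75.96, so 76.

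**2. Truncated records in the same formula.** Power = Φ(√(0.11026 × events) − 1.960), starting from 76. The truncated share is an assumption.

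| Records truncated before return | Events | Power |
|---|---|---|
| 0% | 76 | 82.5% |
| 5% | 72.2 | 80.6% |
| 10% | 68.4 | 78.4% |

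The four added participants therefore cover about 5% of records (3.8 of 76). If instead 5% is missed independently at every visit, simulation leaves about 70.3 events. The formula then gives Φ(√7.751 − 1.960) = Φ(0.824) = 79.5%.

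**3. How each rule uses a gap.** Let S(t) be the probability of not having recovered by t, L the last observed not-recovered visit (time zero if none), and R the first observed recovered visit. Interval censoring contributes S(L) − S(R). Truncation contributes only S(L), or S at the missed visit if censoring is placed there. If T+15 is missed, dropping the participant contributes nothing, while entering a non-recovery contributes S(T+15).

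**4. Simulated size.** Assumptions: n = 76; age uniform with SD 11.25; one covariate with R² 0.2 with age and no effect of its own; log-hazard slope of size 0.033 with older participants slower; cumulative return 75/85/95/98/100% at T+15, T+40 and days 1, 3 and 7. The 75% and the 100% by day 7 come from SAP 10.3 and the rest is assumed. The model is grouped proportional hazards with a two-sided 5% Wald test. Missingness is random at assumed rates. The absolute power levels depend on the model and the curve, so only differences matter.

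T+15 missed (20,000 replicates, Monte Carlo error 0.3 points; full-data power 72.3%):

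| T+15 missed | Dropped | Interval-censored |
|---|---|---|
| 1% | 72.0% | 72.2% |
| 2% | 71.4% | 72.2% |
| 5% | 70.1% | 72.0% |
| 10% | 67.7% | 71.8% |

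Dropping costs 2.2 points at 5% and 4.6 at 10%. The slope changes by +0.5% to +1.2%.

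T+40, day 1 and day 3 missed (8,000 replicates, error 0.5 points; full-data power 71.6%):

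| Missed per visit | Participants truncated | Truncated (last observed visit / missed visit) | Interval-censored |
|---|---|---|---|
| 5% | 1.8 | 70.5 / 70.3% | 71.3% |
| 10% | 3.5 | 69.6 / 69.0% | 71.1% |

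Against interval censoring the cost is 0.8 to 1.0 points at 5% and 1.5 to 2.1 at 10%. The slope stays within about 1%.

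Other recovery tails with 75% at T+15, and 60% or 85% returning at T+15, give losses from dropping of 1.9 to 5.2 points at 5-10% missing.

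**5. Missed = not recovered, later visits kept.** With random T+15 missingness the slope shrinks by 5.8% at 5% and 9.7% at 10%. With T+15 missingness rising with age (assumed logit slope 1 per SD; 5% or 10% at mean age; 400 replicates), the slope becomes 9% or 16% steeper. A separate 300-replicate run at 10% gave about 20% (−0.043 against −0.036). With no true age effect, the 10% case rejected in about 10% of replicates (error about 1.5 points). The scenario can therefore move the slope either way.

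**The case against.** Several points on the other side stand.

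- Censoring at a missed visit is conventional. It is valid under the same condition that interval censoring needs: missing a visit is unrelated to recovery, given the covariates. The preference for interval censoring is about efficiency.
- The documents give no missing rate and expect it to be low. T+15 and T+40 are done on site, so non-attendance there is unlikely.
- The plan already adds four participants, which roughly covers a 5% loss.
- The multiple-imputation step starts above 5%, where the loss becomes visible. It is only to be explored, so this is partial mitigation.
- The GLMMs keep partial data, although they are not the primary test.

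A reader might infer more: that truncation biases the age slope, or that a missed T+15 costs 7 to 14 power points and shrinks the slope by 8% to 15%. Those larger figures do appear in the simulation (64.8% power at 5% missing, 58.4% at 10%), but only when a missed T+15 is entered as an observed non-recovery. The available SAP text does not state that coding. Read literally, truncation leaves such a participant with no post-anesthesia record, which is the dropped case. Nor can one say that the plan has no rule for T+15. The available SAP text begins mid-sentence and relies on Sections 4 and 5.0, which it does not include and which may settle the matter.

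None of this removes two facts: the stated rule leaves observed returns unused, and carry-forward is mislabelled as missing at random.

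**Conclusion.** The point holds as a minor one. The primary rule gives up information that the study will have collected, and the sensitivity analysis carries two incompatible labels. The cost is about 1 to 2 power points for gaps at T+40, day 1 and day 3 at 5-10% each, and about 2 to 5 points if 5-10% miss T+15 and are dropped. It is negligible at 1-2%. No bias in the age effect is shown: under random missingness the slope is essentially unchanged by truncation.

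These sizes rest on assumed missing rates, an assumed recovery curve between T+15 and day 7, and missingness unrelated to outcome. Confidence is high that the rule leaves later returns unused and that the label is wrong. It is moderate for the T+15 part, because the sections that may define its coding are not available.

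**What to change.** In SAP 10.1:

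1. In the primary discrete-time model, keep visits after a gap. Treat the return as interval-censored between the last observed not-recovered visit (time zero if none) and the first observed recovered visit.
2. State that a missed T+15 is not entered as an observed non-recovery.
3. Remove the missing-at-random label from the carry-forward analysis.
4. Keep missed = not recovered as one sensitivity scenario, and do not call it a bound on the age slope. Pair it with the opposite scenario (recovered at the missed visit if recovered at the next) or with multiple imputation under a pre-specified model.

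The cost is a few sentences and a short grouped likelihood, with no new data or visits. The downside is slightly more programming. Interval censoring also still assumes that missing a visit is unrelated to recovery given the covariates, which is why the paired scenarios are needed.
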